**A Registry to Evaluate the Flexitouch System and
Flexitouch Plus for Treatment of Head and Neck
Lymphedema**

Protocol# 4060

24 January 2019

Protocol Version 4.0

Investigator Signature

Protocol Title: A Registry to Evaluate the Flexitouch System and Flexitouch Plus for Treatment of Head and Neck Lymphedema

Protocol Number: 4060

Version: 4.0; 24 January 2019

I confirm that I have read this protocol. I will comply with the protocol and the principles of Good Clinical Practices (GCPs), institutional research policies and procedures, and other appropriate regulatory requirements.

Site Principal Investigator Name (Print)

Site Principal Investigator Signature

Date

SYNOPSIS

Registry Title	A Registry to Evaluate the Flexitouch System and Flexitouch Plus for Treatment of Head and Neck Lymphedema
Protocol Date	24 January 2019
Protocol Version	4.0
Name of Sponsor	Tactile Medical™
Device	Flexitouch system or Flexitouch Plus with Head and Neck Garments
Registry Objective	To evaluate the long term effectiveness of the Flexitouch system and Flexitouch Plus in those with head and neck lymphedema.
Primary Endpoint	Symptom and function improvement
Secondary Endpoints	Changes in QOL, changes in pain, reduction in head and neck swelling, ease of use, treatment satisfaction
Registry Design	This registry is a multi-center, prospective, observational, registry designed to evaluate patients with head and neck lymphedema who receive the Flexitouch system or Flexitouch Plus.
Treatment	Flexitouch Head and Neck Treatment, as prescribed.
Eligibility	
Inclusion Criteria:
 
 • Age ≥ 18 years • A diagnosis of head and/or neck lymphedema • Must be able and willing to participate in all aspects of the registry and provide informed consent prior to registry participation • Head and chest measurements within the following: 
 ○ Crown of head circumference: ≤ 72 cm ○ Chest circumference: ≤ 158 cm • Prescribed the Flexitouch system or Flexitouch Plus 
Exclusion Criteria:
 
 • Uncontrolled hyperthyroidism or parathyroidism (for which endocrinologist recommends against neck compression) • Carotid sinus hypersensitivity syndrome • Symptomatic carotid artery disease, as manifested by a recent transient ischemic attack (within 30 days), ischemic stroke, or amaurosis fugax (monocular visual ischemic symptoms or blindness) • Symptomatic bradycardia in the absence of a pacemaker • Internal jugular venous thrombosis (within 3 months) • Increased intracranial pressure or other contraindications to internal or external jugular venous compression • Acute radiation dermatitis, unhealed surgical scar, unhealed or open wound(s), or surgical flap less than 6-8 weeks post-operative

	
 • Facial or head and neck dermal metastasis • Acute facial infection (e.g., facial or parotid gland abscess) • Any condition in which increased venous and lymphatic return is undesirable • Heart failure (acute pulmonary edema, decompensated acute heart failure) • Subject is pregnant or trying to become pregnant • Acute venous disease (acute thrombophlebitis, acute deep venous thrombosis, acute pulmonary embolism)
Subject Participation Duration	Approximately 6 months
Sample Size	Open

TABLE OF CONTENTS

1.0	Contact Information	7
1.1	Sponsor Contact Information	7
2.0	Abbreviations	7
3.0	Introduction	8
3.1	Background and Rationale	8
3.2	Device Description	8
4.0	Registry Objective	9
5.0	Registry Design	9
5.1	Endpoints	9
5.2	Subject Selection	10
5.3	Registry Duration	11
6.0	Registry Visit Summaries	11
6.1	Screening/Baseline Visit #1	11
6.2	Device Training Visit #2 (Day 0)	11
6.3	Week 2 Phone Call Visit #3 (Day 14±3)	12
6.4	Month 1 Clinic Visit #4 (Day 28±5)	12
6.5	Month 2 Phone Call Visit #5 (Day 56±5)	12
6.6	Month 3 Clinic Visit #6 (Day 84±5)	12
6.7	Month 6 Clinic Visit #7 (Day 168±14)	13
6.8	Registry Exit	13
7.0	Registry Schedule of Activities	14
8.0	Registry Procedures	14

2.0 Abbreviations

AE	Adverse Event
CDT	Complete Decongestive Therapy
CFR	Code of Federal Regulations
CRF	Case Report Form
EDC	Electronic Data Capture
FDA	US Food and Drug Administration
GCP	Good Clinical Practice
HNC	Head and Neck Cancer
HNL	Head and Neck Lymphedema
ICH	International Conference on Harmonization
IRB	Institutional Review Board
MLD	Manual Lymph Drainage
QOL	Quality of Life
ROM	Range of Motion
SAE	Serious Adverse Event
VAS	Visual Analog Scale

3.0 Introduction

3.1 Background and Rationale

Secondary head and neck lymphedema (HNL) is a frequent late effect in patients treated for head and neck cancer (HNC) as the primary cancer or factors related to treatment (surgery, radiation, or chemotherapy) either destroy or obstruct lymphatic vessels and damage adjacent soft tissue.^{1,4} HNL occurs in over 50% of patients receiving radiation and/or surgery for HNC.² HNL may involve external structures (soft tissues of the face, neck, and eyes) or internal structures (oral cavity, mucous membranes, larynx, and pharynx), but most often both are involved simultaneously.³ The resultant clinical impact is dependent on the anatomic sites involved and the extent of associated lymphatic dysfunction. These symptoms can range from mild to severe. The most common areas of external swelling and fibrosis are in the submental region and the neck.^{2,4} In severe cases, HNL may impact critical physical functions (e.g., respiration, mastication, swallowing, communication, and vision). HNL, comparable to lymphedema at other sites, is often associated with psychological distress and degradation to quality of life.^{3,4} In a recent study of 1,202 HNC patients, the majority of patients reported cosmetic concerns and discomfort. More than one third reported functional complaints, including difficulty swallowing (68%) and difficulty breathing (39%).² The most common functional complaint among patients who underwent total laryngectomy was difficulty breathing, often related to tracheostomal obstruction from submental edema.²

Damaged lymphatics result in high-protein fluid collection in the affected tissues. Lymphedema is associated with chronic inflammation, which may lead to a self-perpetuating and progressive course.⁵ HNL patients often experience tightness and discomfort in the muscles of the neck and shoulders which may impede range of motion and function of these muscular groups.³ Damage to the muscles in the affected region may also occur after radiation, resulting in atrophy, weakness, and altered sensation.

The treatment of HNL utilizes modified techniques of in-clinic complete decongestive therapy (CDT), including manual lymph drainage (MLD). Currently, some patients are able to continue simplified versions of these techniques at home, yet, many patients with HNL experience difficulty performing the treatment and/or find the treatment is insufficient in effectively managing their symptoms long-term. Clinicians and patients have therefore identified a need for additional effective options for at home treatment of HNL. In response, Tactile Medical has developed a garment for the treatment of HNL utilizing the Flexitouch system or Flexitouch Plus pneumatic compression device. Tactile Medical seeks to evaluate the long term effectiveness of the Flexitouch system and Flexitouch Plus.

3.2 Device Description

The Flexitouch system and Flexitouch Plus (Tactile Medical™, Minneapolis, MN, USA) are pneumatic compression devices which have been cleared by the Food and Drug Administration (FDA) for market in the US (K153311 and K170216, respectively; US HCPCS code E0652).

[figure not shown]
The Flexitouch® Head and Neck Garment is constructed of nylon and has up to 16 pneumatic chambers covering part of the head, neck, and chest. The device applies brief applications of dynamic pressure in a wave-like manner to the treatment area. Used in conjunction with the Flexitouch controller, the Head and Neck Garment is intended to treat lymphedema affecting the head and neck by stimulating the adjacent axillary lymphatic tributary regions and directing fluid from the affected area to healthy, functioning regions.

4.0 Registry Objective

The objective of this registry is to evaluate the long term effectiveness of the Flexitouch system and Flexitouch Plus in those with head and neck lymphedema. This outcome data will include information regarding each subject’s medical history, symptoms, quality of life, pain, range of motion (ROM), swelling, ease of use, treatment satisfaction, treatment compliance, and device-related adverse events.

5.0 Registry Design

This multi-center, prospective, observational, registry will follow patients with head and neck lymphedema who are using the Flexitouch system or Flexitouch Plus. Data collection will occur at Baseline and Days 14, 28, 56, 84, and 168.

5.1 Endpoints

5.1.1 Primary Endpoints

To evaluate symptom and function improvement after 168 days (approximately 6 months) of treatment with the Flexitouch system or Flexitouch Plus based upon:

- Symptom survey (EORTC H+N35); and
- Range of motion measures (neck, mouth, and shoulder).

5.1.2 Secondary Endpoints

To evaluate quality of life (QOL), pain, swelling, ease of use, and treatment satisfaction after 168 days (approximately 6 months) of treatment with the Flexitouch system or Flexitouch Plus based upon:

- Change in the QOL (EORTC C30);
- Change in pain (VAS);
- Change in swelling (upper neck, lower neck, and ear to ear measurements); and
- Ease of use and treatment satisfaction (survey).

5.2 Subject Selection

The registry population will be drawn from patients who have head and neck lymphedema and are prescribed the Flexitouch system or Flexitouch Plus for in-home treatment of their head and neck lymphedema. Only patients who meet the criteria listed below and have provided informed consent will be considered for participation. Subjects will be considered enrolled in the study after they have signed the Informed Consent Form, met all inclusion/exclusion criteria, and completed the device training visit. Any subjects who do not meet inclusion/exclusion criteria, or do not ultimately receive the device, will be considered screen failures.

5.2.1 Inclusion Criteria

Patients must meet the following criteria:

- Age \geq 18 years
- A diagnosis of head and/or neck lymphedema
- Must be able and willing to participate in all aspects of the registry and provide informed consent prior to registry participation
- Head and chest measurements within the following:
 - Crown of head circumference: \leq 72 cm
 - Chest circumference: \leq 158 cm
- Prescribed the Flexitouch system or Flexitouch Plus

5.2.2 Exclusion Criteria

Patients must not meet any of the following criteria:

- Uncontrolled hyperthyroidism or parathyroidism (for which endocrinologist recommends against neck compression)
- Carotid sinus hypersensitivity syndrome
- Symptomatic carotid artery disease, as manifested by a recent transient ischemic attack (within 30 days), ischemic stroke, or amaurosis fugax (monocular visual ischemic symptoms or blindness)
- Symptomatic bradycardia in the absence of a pacemaker
- Internal jugular venous thrombosis (within 3 months)
- Increased intracranial pressure or other contraindications to internal or external jugular venous compression
- Acute radiation dermatitis, unhealed surgical scar, unhealed or open wound(s), or surgical flap less than 6-8 weeks post-operative

- Facial or head and neck dermal metastasis
- Acute facial infection (e.g., facial or parotid gland abscess)
- Any condition in which increased venous and lymphatic return is undesirable
- Heart Failure (acute pulmonary edema, decompensated acute heart failure)
- Subject is pregnant or trying to become pregnant
- Acute venous disease (acute thrombophlebitis, acute deep venous thrombosis, acute pulmonary embolism)

5.3 Registry Duration

Enrollment will occur at centers throughout the United States. Subjects will remain active in the registry for a period of 168 days (approximately 6 months), and after that time, no additional information will be collected. The duration of the registry has not been specified; however, enrollment will be open for the duration of the registry. Registry analyses will be completed at various times throughout the lifecycle of the project.

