6.7 Month 6 Clinic Visit #7 (Day 168±14)

Approximately 168 days after the subject begins using the prescribed treatment, or upon early termination of a subject (if possible), he or she will return to the clinic and undergo the following procedures at Visit 7:

- Changes to medical history;
- Obtain vital signs (if collected as part of standard of care);
- Complete lymphedema evaluation;
- Obtain ROM measurement (Appendix B);
- Obtain swelling measurements (Appendix C);
- Have subject complete the EORTC C30 (Appendix D), EORTC H+N35 (Appendix E), VAS (Appendix F), and Ease of Use and Treatment Satisfaction Survey (Appendix G);
- Record device-related adverse events (NOTE: Compare events to pre-existing conditions documented in Medical History to determine if the event is a new event, a worsening of a pre-existing event, or just a reoccurrence of a pre-existing event); and
- Review treatment compliance with subject.

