9.0 Subject Withdrawal or Early Termination

Subject participation may be terminated prior to completing the registry for any of the following reasons:

- **Withdrawal of Consent**
Subjects may withdraw their consent to participate at any time. If a subject withdraws consent, previous information that has already been obtained will be available for analysis.
- **Lost to Follow-up**
A certified, return-receipt letter must be sent to the subject after 2 attempts to reach the subject by telephone have failed. The subject will be considered lost to follow-up if this communication is unsuccessful.
- **Adverse Event**
Subject experiences an adverse event that in the investigator's clinical judgement necessitates discontinuation of their participation in this registry.
- **Discretion of the Principal Investigator**
Subjects may be withdrawn at the investigator's discretion in the event of subject noncompliance, changes in the subject's health, or other reasons based on the investigator's clinical judgment.

When a subject withdraws prior to completing the registry, all effort should be made to complete Visit 7 prior to documenting the reason for withdrawal in the subject's medical record.

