15.0 Statistical Methods

For continuous variables, descriptive statistics will include the number of subjects (n), mean, standard deviation, median, inter-quartile range, minimum, and maximum, based upon subjects with reported data for the variable being analyzed.

Frequencies (numerator and denominator), percentages, and 95% confidence intervals will be displayed for categorical data. Percentages by categories will be based on the number of subjects with no missing (unreported) data for the specific variable being analyzed and the count of the patients for each individual level of the categorical variable (the level specific numerators). Percentages will add up to 100%, unless otherwise indicated.

There are no plans to impute missing data and there are no plans to explicitly report missing data (counts and/or percentages) in the tables for all variables as part of the planned study report content. Variations in the reported sample sizes within and/or between relevant tables can be used to ascertain insights into unreported data. In some cases, unreported data may be due to it not being clinically relevant to a particular patient or may represent expected data that was not collected. Selected analyses pertaining to unreported and/or missing data may be discussed and considered as future findings warrant.

The observational nature of the study suggests that the statistical focus will be on estimation and hypothesis generation and not hypothesis testing. Though p-values will be reported as apropos, point estimates, and 95% confidence intervals will be used to guide exploratory analyses for potentially clinically meaningful differences or changes to be discussed and evaluated.

Inter-group (e.g., bivariate) comparisons, when performed, will utilize chi-square, ANOVA, t-test, and appropriate non-parametric tests, unless otherwise specified.

Multivariable models (e.g., linear regression or logistic regression) may be used to assess the predictive relationships and control for possible confounding imbalances of selected multiple variables to specific outcome measures of interest.

Any formal null hypothesis-based statistical comparisons will be made using two sided tests at the $\alpha=0.05$ significance level unless specifically stated otherwise. All null hypotheses will be of no inter-group difference, all alternative hypotheses will be two-sided, unless specifically stated otherwise.

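### Under open enrolment, varying sample sizes cannot show the Day 168 follow-up rate, and early-termination Visit 7 records have no stated place in the 168-day summary

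*Combined protocol and SAP*

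**What the plan says.** The Synopsis gives the sample size as open. Section 5.3 adds "The duration of the registry has not been specified; however, enrollment will be open for the duration of the registry", followed by "Registry analyses will be completed at various times throughout the lifecycle of the project". No section sets a data cut-off, a minimum follow-up or a denominator of subjects due for Visit 7, and none names a final analysis.

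Section 5.1.1 states the primary endpoint as follows: "To evaluate symptom and function improvement after 168 days (approximately 6 months) of treatment". Visit 7 is scheduled for Day 168±14, but Section 6.7 also holds it "or upon early termination of a subject (if possible), he or she will return to the clinic". Section 9.0 reinforces this for withdrawals: "all effort should be made to complete Visit 7 prior to documenting the reason for withdrawal".

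Section 15.0 bases its summaries on subjects who have a value for the variable concerned and plans no imputation. It states that "there are no plans to explicitly report missing data (counts and/or percentages) in the tables for all variables". In place of such counts it offers this: "Variations in the reported sample sizes within and/or between relevant tables can be used to ascertain insights into unreported data". It then gives two possible reasons, worded as examples: "unreported data may be due to it not being clinically relevant to a particular patient or may represent expected data that was not collected". Its last sentence on the subject leaves further missing-data analyses to later discretion.

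**The concern.** Section 15.0 does more than leave a gap. It names varying n as the way to judge unreported data. That can work once every subject has reached Day 168. Under rolling enrolment there is a further reason for an absent value, namely that the visit is not yet due, and Section 15.0 does not mention it. A reader of a given report could not tell poor follow-up from recent enrolment. Because Section 15.0 makes estimation the focus, it matters which subjects an estimate describes and what share of the eligible group they form.

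The second issue does not depend on when the data are cut. A Visit 7 record may come from a subject who left after a few weeks. If every reported Visit 7 value is summarised, shorter treatment durations enter an endpoint defined at 168 days. Section 15.0 neither includes nor excludes these records.

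**Working it through.** The documents give no sample size, exit rate or analysis date, so there is no stated figure to reproduce. What follows is illustration.

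**Inputs from the protocol.** Day 0 is the training date (6.2), and enrolment is complete at that visit (5.2). The Visit 7 window is Day 154 to Day 182 (6.7).

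**Assumptions.** Day 0 is uniform over the T days before the cut. A share of 20% exits before Visit 7 at a constant hazard, with no other loss. Completers attend on average at Day 168. Cuts are at T = 252, 365 and 730 days.

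**1. What n shows when true follow-up is 80%.** Completers with Visit 7 as a share of enrolled = 0.8 × (T − 168)/T:
- T = 252: 0.8 × 84/252 = 0.267
- T = 365: 0.8 × 197/365 = 0.432
- T = 730: 0.8 × 562/730 = 0.616

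**2. The reverse problem.** Suppose Visit 7 n is one third of enrolled. The loss that fits is 1 − (1/3)/[(T − 168)/T]:
- T = 252: 1 − 0.333/0.333 = 0%
- T = 365: 1 − 0.333/0.540 = 38%
- T = 730: 1 − 0.333/0.770 = 57%

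The same n therefore fits very different losses, depending on accrual time. Even a stated cut date would not settle the loss without the Day 0 distribution.

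**3. A due denominator.** Call a subject due when Day 0 is at least 182 days before the cut, whether or not the subject has exited. The due share is (T − 182)/T = 0.278, 0.501 and 0.751. Among due subjects, assessed/due is 0.80 at every cut. The numerator must be limited to due subjects. Dividing all completers' records by the number due would give 0.267/0.278 = 0.96, 0.432/0.501 = 0.86 and 0.616/0.751 = 0.82.

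**4. Pooling early-termination records.** The hazard is λ = −ln(0.8)/168, so 1/λ = 752.9 days. Completers are proportional to 0.8(T − 168). Exits are proportional to 0.2(T − 168) + (168 − 0.2/λ) = 0.2(T − 168) + 17.4. If exits improve 0.5 SD less, the pooled mean differs from the completers' mean by 0.5 × exit share.

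| | T = 252 | T = 365 | T = 730 | Mature |
|---|---|---|---|---|
| Exit share, all exits attend | 0.337 | 0.265 | 0.224 | 0.200 |
| Shift from completers (SD) | 0.17 | 0.13 | 0.11 | 0.10 |
| Part due to cut timing (SD) | 0.07 | 0.03 | 0.01 | 0 |
| Exit share, half attend | 0.203 | 0.153 | 0.126 | 0.111 |
| Part due to cut timing, half attend (SD) | 0.05 | 0.02 | 0.01 | 0 |

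The part due to timing is 0.5 × (exit share − mature exit share).

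Mean exit day when mature is 1/λ − 168 × 0.8/0.2 = 752.9 − 672 = 80.9. The mature pooled mean follow-up is 0.8 × 168 + 0.2 × 80.9 = 150.6 days, against 134, 143 and 148 days at the three cuts. The model counts every exit before Day 168 as early; the few between Days 154 and 168 would in fact fall in window.

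**5. Cost of restricting estimates to closed windows.** With Visit 7 uniform over Days 154 to 182, the share of valid in-window records set aside is 14/(T − 168): 14/84 = 17%, 14/197 = 7% and 14/562 = 2.5%.

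**The case against.** **Section 5.3 does not say that 168-day summaries will be run on immature data.** Analyses during the registry could cover baseline, Day 28, Day 84 or safety data. This stands. A reader might infer a planned immature 168-day analysis, but the text shows only that no rule prevents one.

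**Section 15.0 claims little for varying n.** It speaks of insights, not of a follow-up rate, and its two causes are offered as examples. The phrase about tables for all variables could leave room for a disposition table, and later missing-data analyses are allowed. All this is fair, but none of it commits to a count of subjects due, and discretionary later work does not supply one.

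**Most of the bias has nothing to do with cut timing.** This stands. At the 252-day cut, 0.10 of the 0.17 SD is present when the data are mature, and timing adds less at later cuts. The SD figures also assume that every exit attends, whereas Section 6.7 says only if possible and Section 9.0 exits include subjects lost to follow-up.

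**The data to separate the groups are already collected.** This is true and makes the remedy cheap. It does not put the counts into the report.

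**A mandatory closed-window restriction on the estimates is not needed.** This stands. It discards valid in-window records and, under the model used here, corrects no bias in the in-window mean.

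**Conclusion.** The concern holds as two separate points, both worth correcting and neither fatal to a descriptive registry.

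First, for any 168-day summary made during follow-up, n cannot separate not-yet-due from exited or missed subjects. Under the stated assumptions, 80% follow-up looks like 27%, 43% or 62%. The ambiguity shrinks as the registry ages but is still visible at two years. It would vanish once every subject's window had closed.

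Second, at any cut including a final one, the place of early-termination Visit 7 records in the 168-day estimate is undefined. If they are pooled, the mature shift is 0.10 SD with all exits attending (0.5 × 0.111 = 0.06 SD with half), and mean follow-up is about 151 days instead of 168.

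Two stronger readings are not supported. A reader might infer that the plan does pool these records, but Section 15.0 is silent. A reader might also infer that repeated cuts by themselves seriously bias the estimate; timing adds at most 0.07 SD here, and only at a 252-day cut that the documents do not mention. The omissions are certain. Their size rests on assumed accrual, exit, attendance and effect difference.

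**What to change.** In Section 15.0, replace the reliance on varying sample sizes with a table, at each stated data cut and for each visit, of subjects:
- enrolled;
- due, meaning that the visit window has closed (for Visit 7, Day 0 at least 182 days before the cut), with exited subjects kept in the count;
- assessed in window;
- exited early, with and without a Visit 7;
- missed.

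Report the follow-up rate as assessed/due, with the numerator taken from due subjects only. Show early-termination Visit 7 records that fall outside Day 168±14 on a separate row, and keep them out of the 168-day estimate.

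Restricting the 168-day estimates themselves to subjects with closed windows is optional, for example as a sensitivity analysis. It would set aside about 17%, 7% and 2.5% of valid in-window records at the three illustrative cuts.

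The cost is wording and slightly more tabulation. No new subjects, visits or data are needed: Day 0 (6.2), visit windows (7.0), and exit date and reason (6.8) are already recorded.
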